4.3 Study Endpoints

Safety

Adverse events, concomitant medications, physical examinations including detailed neurological examination, vital signs, weight, 12-lead electrocardiograms (ECGs), clinical laboratory evaluations (including clinical chemistry, hematology, and urinalysis), CSF safety evaluations, MRI of the brain, and Columbia-Suicide Severity Rating Scale (C-SSRS)

Pharmacokinetics

- Pharmacokinetic parameters of WVE-003 in plasma at predefined time points
- Concentration of WVE-003 in CSF at predefined time points

Pharmacodynamics

- Change from baseline in the level of mHTT protein in CSF
- Change from baseline in the level of tHTT protein in CSF
- Change from baseline in the level of wtHTT protein in CSF
- Change from baseline in the level of NfL in CSF
- Change from baseline in the level of exploratory biomarkers in CSF, plasma, and/or PBMCs

Clinical Effects

- Change from baseline in the UHDRS Total Functional Capacity (TFC)
- Change from baseline in UHDRS total motor score
- Change from baseline in the UHDRS independence scale
- Change from baseline in Symbol Digit Modalities Test (SDMT)
- Change from baseline in Stroop word reading test
- Change from baseline in the composite UHDRS
- Change from baseline in the PBA-s
- Changes from baseline in MRI of the brain

4.4 Safety Considerations

4.4.1 Dose Escalation Committee Review

The DEC will be responsible for making recommendations regarding dose escalation in Period 1, initiation of multiple dosing in Period 2, and subsequent dose escalation in Period 2. The DEC will review blinded data. All recommendations of this committee will be reviewed by the SMC, which makes the final recommendation.

4.4.1.1 Period 1 – Dose Escalation

After all patients in a Period 1 cohort have received study drug and completed 2 weeks of postdose follow-up, the DEC will review the available blinded safety and PK data. The DEC will determine if it is safe to proceed with the next single-dose cohort. Based on data review, the DEC may decide to add additional cohorts or select alternate dose levels for any of the cohorts.

[figure not shown]

4.4.1.2 Initiation of Period 2

The DEC will review the available safety and PK data and decide if Period 2 (i.e., P2C1) can be initiated. **Note that Period 2 will not be initiated until this Substantial Amendment to the IMPD with the supportive nonclinical data is approved by the local regulatory authorities.**

4.4.1.3 Period 2 – Subsequent MAD Cohorts (P2C2 and P2C3)

Once 6 patients in the current cohort have received at least 2 consecutive doses, the DEC will review the available blinded safety and PK data and determine if it is safe to proceed with the subsequent multiple-dose cohort. Based on data review, the DEC may decide to add additional cohorts, select alternate dose levels (including lower doses), reduce the number of doses or reduce the frequency of dose administration for any of the cohorts, or change the number of patients planned for a cohort.

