
Dose Escalation Committee Review
 
The DEC will be responsible for making recommendations regarding dose escalation in Period 1, selection of the initial dose level in Period 2, and subsequent dose escalation in Period 2.
 
Period 1 Dose Escalation: After all patients in a Period 1 cohort have received study drug and completed 2 weeks of postdose follow-up, the DEC will review the available safety and PK data. The DEC will determine if it is safe to proceed with the next SAD cohort.
 
Initiation of Period 2: The DEC will review the available safety and PK data and decide if Period 2 (i.e., P2C1) can be initiated. Note that P2C1 will not be initiated until repeat-dose toxicity data have been submitted to and approved by the local regulatory authorities.
 
Period 2 – Subsequent MAD Cohorts (P2C2 and P2C3): Once 6 patients in the current cohort have received at least 2 consecutive doses, the DEC will review the available safety and PK data and determine if it is safe to proceed with the subsequent multiple-dose cohort. The DEC may also choose to reduce the number of doses in a cohort or reduce frequency of dose administration based upon their review.
 
Based on data review, the DEC may decide to add additional cohorts in either Period 1 or Period 2, select alternate dose levels (including lower doses) for any of the cohorts, or change the number of patients planned for a cohort.
 
The DEC will review blinded data. All recommendations of this committee will be reviewed by the SMC, which makes the final recommendation.
 
Safety Monitoring Committee Review: In addition to reviewing the DEC's decisions, the SMC will review unblinded aggregate safety data periodically and on an ad hoc basis throughout the study. The SMC will review any SAEs that occur in sentinel patients in order to determine if the cohort should continue or if a lower dose should be selected. In addition, if treatment-emergent adverse events (TEAEs) occur that meet the Stopping Criteria, the SMC will review the unblinded safety data and determine whether it is safe to proceed with the cohort or if a lower dose should be explored.
 
If the stopping criteria are met at any point in the study, enrollment and dosing will be suspended until the data are reviewed. Similarly, if an SAE occurs in the sentinel patients in a cohort, no additional patients will be dosed in that cohort until the safety data are reviewed.
 
Single Dose Stopping Criteria: During Period 1, dosing of patients in a cohort will be suspended:
 
• If a single patient experiences an SAE assessed as related to study drug;			

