Within 1 week prior to performing any lumbar puncture, a blood sample will be tested locally for platelet count and prothrombin time to confirm that it is safe to proceed with the lumbar puncture. Other predose assessments may also be performed up to 1 week prior to dosing as specifically listed in [Table 3](#) including UHDRS, PBA-s, and weight.

The Period 2 MAD cohorts will be conducted in a sequential manner. Subsequent multiple-dose cohorts will not initiate until the criteria for dose escalation are met ([Section 4.4.1.3](#)).

Immediately after study drug administration in any cohort, all patients should be ambulatory and active for approximately 30 minutes postdose on all dosing days. The Investigator should note any weakness or fatigue during this period. Formal physical examinations targeting the neurological system will be performed postdose at the time points specified in [Table 3](#).

Patients will attend clinic visits Q4W for assessments of safety, PK, and PD. Patients in P2C1 will receive doses on Week 0, Week 8, and Week 16. Pending DEC/SMC recommendation, subsequent cohorts may receive doses Q8W or less frequently (e.g., on Week 0 and Week 12).

4.1.4.4 *Period 2 Follow-up*

All patients are required to complete follow-up assessments, including evaluations of safety, PD, PK, clinical effects, and MRI. Patients will be followed up for a minimum of 12 weeks after the last dose. Any postdose SAEs will be monitored until resolution.

4.1.5 *Early Termination Visit*

If a patient withdraws from the study early, the patient should complete an early termination visit. Refer to [Section 5.3](#) for information on early withdrawal from study drug or from the study.

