Abbreviations: CBC = complete blood count; CRP = C-reactive protein; CSF = cerebrospinal fluid; D = day; ECG = electrocardiogram; ET = early termination; h = hour; m = minute; PBMC = peripheral blood mononuclear cell; PD = pharmacodynamic(s); PK = pharmacokinetic; W = week.

^a Predose on all dosing days, CSF sample will be collected approximately 15 minutes prior to study drug administration. At all noted time points, approximately 20 mL of CSF total should be collected. CSF samples must be tested locally for safety for the following parameters: total protein, glucose, and cell counts (white blood cell counts with differential) on all noted visits.

^b This lumbar puncture is optional for patients who terminate early.

- Electrocardiogram recordings will be obtained in the supine position after the patient has rested comfortably for ≥ 10 minutes. At time points when plasma PK is also being collected, the ECG should be performed first, and PK should be collected within 30 minutes after (and within the applicable postdose window).
- Parameters to be assessed are detailed in [Table 6](#). Clinical laboratory safety assessments will be performed up to 1 week prior to dosing on all dosing days. Note that these assessments also include CBC, CRP, complement, and fibrinogen.
- Assessments from the last in-clinic visit in Period 1 may be used if the last in-clinic visit occurred within 4 weeks prior to the Confirm Eligibility visit for Period 2.

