Period 1 Urine PK: Samples will be collected on Week 0/Day 1 from 0-4 hours, 4-8 hours, and 8-24 hours postdose.

Period 1 CSF PK: Samples will be collected predose on Week 0/Day 1, as well as Week 2, Week 4, Week 8, and Week 12. A sample will also be collected at the ET visit, if the patient discontinues early.

Period 2 Plasma PK: At the first and last dosing visit, blood samples will be collected predose (within 4 hours prior to dosing), and postdose at 30 minutes (± 5 minutes), 1 hour (± 15 minutes), 2 hours (± 15 minutes), 4 hours (± 30 minutes), and 6 hours (± 30 minutes). New patients only will also have a sample collected on Day 1 at 24 hours (± 2 hours) postdose. For any other dosing visit, blood samples will be collected at 2 hours (± 1 hour) postdose. In addition, plasma PK samples will be collected once at all non-dosing clinic visits. A sample will also be collected at the ET visit, if the patient discontinues early.

Period 2 CSF PK: Samples will be collected at all clinic visits (Week 0/Day 1, Week 4, Week 8, Week 12, Week 16, Week 20, Week 24, and Week 28). The sample will be collected predose on dosing visits. A sample will also be collected at the ET visit, if the patient discontinues early.

The date and time of the sample collection will be recorded.

Samples will be analyzed by a central laboratory to determine concentrations of WVE-003 using validated methods (plasma and CSF) or qualified methods (urine).

Samples will only be used by the Sponsor and/or a contracted vendor for research related to the development of treatments for HD and stored for a maximum of 10 years. All biological material will be stored and secured in a way that ensures that unauthorized access is prohibited and the samples are not lost, deteriorated, or destroyed accidentally or illegally. Detailed instructions for sample collection, storage, processing, and shipping will be provided in the Laboratory Manual.

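### The review that can release the next multiple-dose cohort requires no follow-up after dose 2, so it guarantees a post-dose-2 CSF safety sample in none of its six patients

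*Combined protocol and SAP*

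**What the plan says.** Section 4.4.1.3 governs the move from one multiple-dose cohort to the next: "Once 6 patients in the current cohort have received at least 2 consecutive doses, the DEC will review the available blinded safety and PK data". On that basis the committee decides whether the next cohort can safely start. The synopsis uses the same trigger: "Once 6 patients in the current cohort have received at least 2 consecutive doses, the DEC will review the available safety and PK data". Neither place sets a minimum time, visit or sample after the second dose.

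The Period 2 schedule determines what can have been observed by then:

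- Section 4.1.4.3 places the P2C1 doses at Weeks 0, 8 and 16 and sets the visit interval: "Patients will attend clinic visits Q4W for assessments of safety, PK, and PD".
- Section 8.3 lists Period 2 CSF collection at the four-weekly visits and adds: "The sample will be collected predose on dosing visits". Table 4, footnote a, puts the draw about 15 minutes before the injection.
- The same footnote makes each CSF draw a safety test: "CSF samples must be tested locally for safety for the following parameters: total protein, glucose, and cell counts".
- For the full blood panel, a Table 4 footnote says: "Clinical laboratory safety assessments will be performed up to 1 week prior to dosing on all dosing days".

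The Period 1 rule in Section 4.4.1.1 is different. The DEC reviews after every patient in the cohort has been dosed and has two weeks of follow-up. Week 2 is also a Period 1 CSF visit (Section 8.3), so that rule coincides with a CSF sample taken after dosing.

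**The concern.** Period 2 is this product's first repeat dosing in patients, and the review in Section 4.4.1.3 decides whether repeat dosing is safe enough to open the next cohort. A silent effect of the second dose, such as a rise in CSF protein or cell count, shows only in a sample taken after that dose. The trigger counts doses given and says nothing about observation after them. As written, the review can be held before any of the six has had a CSF sample or full blood panel that reflects dose 2. The sponsor wrote a follow-up floor for single doses but none for repeat doses.

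**Working it through.** The plan gives no figure to reproduce here. Section 11.1 says the sample size does not rest on hypothesis testing, and the trigger has no stated statistical basis. The check is date arithmetic on the Period 2 schedule.

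**Inputs from the protocol.** Dose 2 in P2C1 is at Week 8, D57 (±3). The next CSF visit is Week 12, D85 (±3) (Table 3; Sections 4.1.4.3 and 8.3). CSF and the full blood panel at a dosing visit are taken before the dose.

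**Step 1: gap from dose 2 to the first CSF safety sample that can reflect it.**

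- Nominal: 85 − 57 = 28 days.
- Shortest within windows: (85 − 3) − (57 + 3) = 82 − 60 = 22 days.
- Longest within windows: (85 + 3) − (57 − 3) = 88 − 54 = 34 days.
- For a later cohort dosed at Weeks 0 and 12, an example the protocol gives: 113 − 85 = 28 days.

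**Step 2: what the rule guarantees.** The required wait after dose 2 is 0 days and the shortest gap is 22 days. The guaranteed number with the sample is 0 of 6. Copying the 14-day wait from Period 1 would still guarantee 0 of 6, because 14 < 22.

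**Step 3: what might happen in practice.** The protocol gives no accrual rate or review date, so both are assumed. Let the six reach dose 2 at equal spacing of *d* days, with the review *L* days after the sixth patient's dose 2. Patient *i* then has (6 − *i*) × *d* + *L* days after dose 2, and has the sample if this is at least 28. For example, with *d* = 7 and *L* = 0 the values are 35, 28, 21, 14, 7 and 0, so 2 of 6 have it.

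| Review held | d = 3.5 | d = 7 | d = 10 | d = 14 | d = 28 |
|---|---|---|---|---|---|
| Same day (L = 0) | 0 | 2 | 3 | 4 | 5 |
| 14 days later | 2 | 4 | 4 | 5 | 5 |
| 28 days later | 6 | 6 | 6 | 6 | 6 |

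**Step 4: sensitivity to visit windows (L = 0).** With the sample at 22 days the same-day row is 0, 2, 3, 4, 5. With the sample at 34 days it is 0, 1, 2, 3, 4. In a same-day review the sixth patient cannot have the sample at any spacing, so 5 is the maximum.

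**The case against.** The strongest case against this is that other protections cover the gap.

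- **Cross-cohort halt.** Section 4.4.3.2 stops dosing in ongoing higher-dose cohorts if the stopping rule is met in a lower-dose one, so late toxicity can still halt a cohort already opened. But the rule needs two patients with an at-least-possibly-related SAE, or two with such a non-serious severe TEAE. Section 8.2 makes a clinically significant abnormal result a recordable AE, but a silent CSF change need not reach either threshold.
- **Dosing sequence.** The next cohort cannot start before the trigger, and its own second dose comes at least 8 weeks later: 56 days nominal, 53 at the window limit (54 − 1). The sixth patient's Week 12 CSF is due by day 34. With visits on schedule, all six samples are therefore drawn before anyone in the next cohort has a second Period 2 dose. This stands, and it confines the exposure mainly to the next cohort's first dose. Single doses up to 90 mg were judged acceptable in Period 1 (Section 2.1), but later dose levels are not stated, and an active rollover patient's first Period 2 dose is already a second exposure.
- **Two-stage review.** The DEC may wait, and the SMC makes the final recommendation (Section 4.4.1) after unblinded data have been prepared (Section 11.3.6). A same-day release is therefore unlikely. But no minimum of data after dose 2 is stated for either committee.
- **Other data.** Each patient in a Q8W cohort has about 8 weeks of follow-up after the first Period 2 dose, with CSF at Week 4 and predose at Week 8. For an active rollover patient these samples already follow a second exposure, though after a washout of at least 12 weeks. Dosing days include neurological examinations at 1 and 4 hours and vital signs at 4 hours (Table 3 footnotes), and patients have a 24-hour telephone line (Section 9.1). These detect same-day or symptomatic effects, or effects of earlier doses.
- **Cumulative dose.** The P2C1 total of 90 mg equals the highest single dose tested (Section 2.1). This is specific to P2C1, while the same trigger also governs release of P2C3.
- **Unseen text.** Text beside the references to Section 4.4.1.3 in Sections 2.1 and 2.3 is redacted, and the DEC and SMC charters are not in the documents. A follow-up condition could sit there. This limit stands.

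**Conclusion.** The concern holds on the visible text. The guaranteed number of patients with a CSF safety sample after dose 2 is 0 of 6, and the first such sample is due 28 days after that dose (22 to 34). These figures come from the protocol alone. The counts by spacing rest on assumed equal spacing and assumed review dates. The same-day row is a floor, not a forecast, and at nominal visit timing the problem disappears if the review is held 28 days after the sixth patient's dose 2.

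The safeguards limit the consequences without replacing the missing minimum. This is a worthwhile, inexpensive improvement to an escalation rule, not evidence that patients are unprotected. Confidence is medium because of the redactions and the unseen charters.

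**What to change.** In Section 4.4.1.3 and the synopsis, keep the count of six and the two-dose requirement, and add a second condition: *and have completed the first scheduled visit after the second dose (Week 12/Day 85 for P2C1), including the CSF safety sample*. Leave the DEC and SMC roles unchanged. If the charters already contain such a condition, state it in the protocol.

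Tie the condition to the next scheduled visit rather than to the two weeks used in Period 1, because Period 2 has no two-week visit. The wording also fits a cohort dosed at Weeks 0 and 12, where that visit is Week 16/Day 113.

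The cost is time: the earliest possible review moves by about 4 weeks (22 to 34 days), or not at all if it would in any case follow the sixth patient's Week 12 visit. No visit, lumbar puncture or patient is added. In P2C1 the new trigger still falls nominally 113 − 85 = 28 days before the sixth patient's third dose at Week 16.

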4.4.2 Safety Monitoring Committee Review

In addition to reviewing the DEC's decisions, the SMC will review unblinded aggregate safety data periodically and on an ad hoc basis throughout the study. The SMC will review any SAEs that occur in sentinel patients in order to determine if the cohort should continue or if a lower dose should be selected. In addition, if TEAEs occur that meet the Stopping Criteria, the SMC will review the unblinded safety data and determine whether it is safe to proceed with the cohort or if a lower dose should be explored.

If the stopping criteria are met at any point in the study, enrollment and dosing will be suspended until the data are reviewed. Similarly, if an SAE occurs in the sentinel patients in a cohort, no additional patients will be dosed in that cohort until the safety data are reviewed. Details on communication of safety concerns are detailed in [Section 4.4.4](#).

4.4.3 Stopping Criteria

4.4.3.1 Single Dose Stopping Criteria (Cohort Stopping Criteria)

During Period 1, dosing of patients in a cohort will be suspended:

- If a single patient experiences an SAE assessed as related to study drug;
- If 2 patients experience a severe TEAE that is assessed as related to study drug; or
- If 4 patients experience a non-serious moderate or severe TEAE within the Medical Dictionary for Regulatory Activities (MedDRA) High Level Group Term (HLGT) *Spinal cord and nerve root disorders*, assessed as related to study drug.

Notification of dose suspension for a given cohort will be made in accordance with applicable regulations. If a determination is made to resume the study, information will be submitted to the regulatory authorities in accordance with local regulations (e.g., substantial amendment) prior to restarting treatment.

4.4.3.2 Period 2 Stopping Criteria

During Period 2, either of the following will result in a dosing halt within the cohort and trigger assessment by the SMC to decide the safe dose level in Period 2:

- If 2 patients in a cohort experience an SAE assessed as at least possibly related to study drug.
- If 2 patients in a cohort experience a non-serious severe TEAE assessed as at least possibly related to study drug.

In addition, dosing will be stopped in any ongoing higher dose cohorts if the stopping rule is met in a lower-dose Period 2 cohort.

Notification of dose suspension for a given cohort will be made in accordance with applicable regulations. If a determination is made to resume the study, information will be submitted to the regulatory authorities in accordance with local regulations (e.g., substantial amendment) prior to restarting treatment.

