4.1.4 Period 2 (Multiple-ascending-dose Period)

Period 2 will not be initiated until this Substantial Amendment to the IMPD with the supportive nonclinical data is approved by the local regulatory authorities. Following this approval, the Sponsor intends to initiate Period 2. The Sponsor will communicate this approval (in writing) directly to the study sites.

the DEC/SMC recommended that Period 2 can initiate at a dose level of 30 mg Q8W.

4.1.4.1 *Period 2 Assessment of Continued Patient Eligibility*

Before initiation of Period 2, the Investigator should confirm patient eligibility to continue in the study ([Section 4.2](#)). If any clinically significant medical findings are observed that, in the judgment of the Investigator (and in consultation with the Sponsor), would make the patient unsuitable for continued participation in the study and/or completion of the study procedures, the patient may not be allowed to participate in Period 2. Applicable evaluations and tests from the last in-clinic visit in Period 1 may be used if the last in-clinic visit occurred within 4 weeks prior to the Confirm Eligibility visit for Period 2. Patients who are considered eligible and have completed at least through Period 1 Week 12/Day 85 may participate in Period 2. New patients will be screened for eligibility.

4.1.4.2 *Period 2 Treatment Assignment*

Patients in P2C1 will receive 30 mg WVE-003 or placebo administered Q8W. Approximately 24 patients will be enrolled in P2C1. Dose levels and cohort sizes for Period 2 subsequent cohorts will be determined by the DEC/SMC, based on previous Period 2 cohort data. Doses will be administered no more often than Q8W through Week 16 (maximum of 3 doses). █

All patients from Period 1 will have the opportunity to roll into Period 2 and will receive up to 3 additional doses of WVE-003 or placebo. Patients will not be re-randomized and will continue to receive active drug or placebo based on Period 1 treatment assignment. Patients will roll into the current Period 2 cohort, irrespective of Period 1 dose level.

Patients may be replaced in accordance with the requirements for dose escalation. Future DEC/SMC recommendations may include the addition of new Period 2 patients. All new patients in Period 2 will receive up to 3 doses of WVE-003 administered no more often than Q8W.

4.1.4.3 *Period 2 Treatment*

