4.4.3.3 Individual Stopping Criteria

Dosing will be stopped for an individual patient at any time in the study if:

- A patient experiences a serious or intolerable adverse event (AE) that, in the Investigator's opinion, requires study drug discontinuation.
- A patient experiences a TEAE that is severe in intensity and related to administration of WVE-003 (except TEAEs associated with lumbar puncture).

The patient will be followed up for safety per protocol. Per the Investigator's judgement, the patient may be allowed to resume participation in the study if or when the event has resolved]. Dosing may be resumed for individual patients upon recovery from the severe event and if supported by the Investigator, based on their assessment of the benefit/risk balance for the patient.

4.4.3.4 *Adverse Events That are Exempt from Stopping Criteria*

Intrathecal administration of drugs is known to result in untoward effects such as post-lumbar puncture headache, pain, etc.^{33,34} Given the common occurrence of such side effects following lumbar puncture, it is anticipated that patients may experience AEs temporal to the IT administration procedure that are not attributable to study drug^{33,34}. Therefore, the AE terms listed in [Table 5](#) will be exempted from the assessment of Stopping Criteria:

Table 5 Adverse Event Preferred Terms Exempted From Stopping Criteria

Preferred Terms Exempt From Stopping Criteria	
Administration site bruise	Instillation site bruise
Catheter site bruise	Post-lumbar puncture syndrome
Infusion site bruising	Post-procedural discomfort
Infusion site discomfort	Post-procedural contusion
Infusion site pain	Procedural headache
Injection site bruising	Procedural pain
Injection site discomfort	Traumatic lumbar puncture
Injection site pain	

Abbreviations: AE = adverse event; MedDRA = Medical Dictionary for Regulatory Activities; PT = Preferred Term.

Note: AEs exempted from the Stopping Criteria include the MedDRA PTs listed above and their associated verbatim terms.

While these procedural events are exempt from Stopping Criteria review, they will be recorded as AEs as described in [Section 9](#). In addition, as part of their ongoing review of unblinded safety data, the SMC will carefully review the above-referenced exempted AE terms to ensure there are no meaningful imbalances between treatment groups.

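### The Period 2 cohort stopping rule keeps serious and non-serious severe events in separate counts, so a graver pair of events can fail to halt dosing where a less grave pair does

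*Combined protocol and SAP*

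**What the plan says.** Section 4.4.3.2 (Period 2 Stopping Criteria) states that "either of the following will result in a dosing halt within the cohort and trigger assessment by the SMC". There are two criteria. The first counts serious events: "If 2 patients in a cohort experience an SAE assessed as at least possibly related to study drug". The second has the same threshold but counts only severe events that do not qualify as serious: "If 2 patients in a cohort experience a non-serious severe TEAE assessed as at least possibly related to study drug".

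The synopsis repeats both. The same section stops any ongoing higher-dose cohort if the rule is met in a lower-dose one, and requires a submission to the regulatory authorities before treatment restarts. Lumbar-puncture terms listed in Table 5 are exempt.

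Period 1 is written differently. Section 4.4.3.1 suspends dosing on a lone serious event: "If a single patient experiences an SAE assessed as related to study drug". Its separate count of severe events is not restricted to non-serious ones: "If 2 patients experience a severe TEAE that is assessed as related to study drug; or". A further Period 1 criterion concerns spinal cord and nerve root disorders.

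For the size of the first Period 2 cohort, Section 4.1.4.2 says: "Approximately 24 patients will be enrolled in P2C1".

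**The concern.** A stopping rule should not become less likely to fire when one of the events gets worse. Here it can. Take two patients, each with a related non-serious severe TEAE: the cohort halts. Make one of those events serious as well as severe. It leaves the second count and becomes a single entry in the first, both counts stand at 1, and the rule is silent. This compares two event profiles; it does not mean that a halt already in force is lifted.

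At stake is the mandatory halt and Safety Monitoring Committee (SMC) assessment in a first-in-human study of repeated intrathecal dosing. If the rule is not met, the rest of the cohort can go on being dosed, and the automatic stop on higher-dose cohorts does not operate either.

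The higher SAE threshold in Period 2 (two patients, against one in Period 1) is a permissible choice and is not questioned here.

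**Working it through.** **The logic.** Let *A* be the number of patients in a cohort with a related SAE and *B* the number of other patients with a related non-serious severe TEAE. As written, the cohort halts if *A* ≥ 2 or *B* ≥ 2. With pooled counts it would halt if *A* + *B* ≥ 2.

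| *A* | *B* | As written | Pooled |
|---|---|---|---|
| 0 | 1 | no halt | no halt |
| 1 | 0 | no halt | no halt |
| 0 | 2 | halt | halt |
| 2 | 0 | halt | halt |
| 1 | 1 | **no halt** | **halt** |

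Only (1,1) differs. With three affected patients, one count must reach 2, so the effect is a delay of one patient.

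**Does anything else force a halt at (1,1)?**

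- Sentinel SAE hold (Sections 4.4.2 and 4.4.4): sentinel patients are described only for Period 1.
- SMC review (Section 4.4.2): "the SMC will review unblinded aggregate safety data periodically and on an ad hoc basis throughout the study". For this pattern that is discretionary.
- Individual stopping (Section 4.4.3.3): applies when "A patient experiences a TEAE that is severe in intensity and related to administration of WVE-003". It covers only the affected patient, and dosing may later resume.
- Dose Escalation Committee review (Section 4.4.1.3): uses blinded data and governs the move to the next cohort.

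None is an automatic cohort halt.

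**Size, as illustration.** The plan gives no operating characteristics for the rule, so there is no figure to reproduce. Inputs: *n* = 24 (Section 4.1.4.2), because the rule counts all patients in the cohort, and assumed per-patient rates *a* (related SAE) and *b* (related non-serious severe TEAE), taken as mutually exclusive and independent between patients. With *q* = 1 − *a* − *b*:

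- Pooled halt = 1 − *q*^24 − 24(*a*+*b*)*q*^23
- Gap, exactly one of each = 24 × 23 × *a* × *b* × *q*^22
- Halt as written = pooled − gap

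At 5%/5%, *q* = 0.90. Pooled = 1 − 0.0798 − 0.2127 = 0.708. Gap = 552 × 0.0025 × 0.0985 = 0.136. As written = 0.572. A simulation of 400,000 cohorts gave the same 0.708 and 0.572.

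| *a* / *b* | As written | Pooled | Gap | Gap ÷ pooled |
|---|---|---|---|---|
| 2% / 2% | 0.159 | 0.249 | 0.090 | 36% |
| 5% / 5% | 0.572 | 0.708 | 0.136 | 19% |
| 2% / 8% | 0.621 | 0.708 | 0.087 | 12% |
| 1% / 9% | 0.659 | 0.708 | 0.049 | 7% |
| 10% / 10% | 0.926 | 0.967 | 0.041 | 4% |

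The last column is the share of cohorts with two or more affected patients in which the written rule does not halt.

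**Deleting the word alone.** If a share *f* of related SAEs is graded severe, deleting 'non-serious' recovers *f* × gap:

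- 5%/5%: 0.640 (*f* = 0.5), 0.674 (*f* = 0.75), 0.708 (*f* = 1)
- 2%/8%, *f* = 0.5: a gain of 0.044
- 1%/9%, *f* = 0.5: a gain of 0.024

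**The case against.** The strongest reply is that this is a narrow gap with little residual risk. SAEs reach the sponsor within 24 hours, the SMC sees unblinded data and can meet ad hoc, and both patients in the pattern would be stopped individually if the event is judged related. Further detail may sit in the SMC charter, which is not among the documents. All of this stands, and it is why the point is a recommended correction and not a critical flaw. It does not supply a mandatory halt.

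Second, the pooled figures overstate what deleting one word achieves, because seriousness and severity are different scales; Section 9.4, for instance, has any overdose recorded as an SAE. Equal rates in the two counts also give the largest gap for a given total. Both points are correct. The *f*-scaled gains and the unequal-rate rows are the fairer guide to the simple edit. A patient with both event types would count in both, which the calculation ignores and which makes a halt likelier.

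Third, more halts are not a benefit in themselves. The count includes placebo patients, and causality is judged blind, so background events can trigger a halt, with a regulatory submission before restart. This cost is real. But the sponsor already accepts it for two non-serious severe events, and the added halts follow patterns at least as grave.

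Fourth, Period 1 refers to events as related, whereas Period 2 uses at least possibly related, and Table 8 does not say whether a possible relationship counts as related. The contrast between periods is therefore clean only for events that meet both descriptions. The inversion inside Period 2 does not depend on it.

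Finally, it may be said that this is only threshold-setting. How many events should halt a cohort is a judgement; a rule that falls silent when one event becomes more serious is an inconsistency whatever the threshold.

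**Conclusion.** The concern holds. As written, one related severe SAE and one related non-serious severe TEAE, in different patients of the same Period 2 cohort and outside the Table 5 exemptions, do not halt dosing, while two related non-serious severe TEAEs do. This follows from the wording and needs no assumed rates.

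The consequence is bounded: one pattern, a delay of one affected patient, and events that would still be reported and seen. Under the assumed rates, the written rule falls short of pooled counts by 0.04 to 0.14 in halt probability for a cohort of 24. The gain from deleting the word alone is smaller in proportion to the share of SAEs graded severe. The correction should be made, because it removes a safety inconsistency with a very small edit.

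**What to change.** Delete 'non-serious' from the second Period 2 criterion in Section 4.4.3.2 and in the synopsis, so that two patients with an at least possibly related severe TEAE, serious or not, halt the cohort. Leave the SAE criterion unchanged. If the sponsor also wants to cover SAEs that are not graded severe, count related SAEs and related severe TEAEs together toward two patients.

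The edit changes no assessments, visits or sample size, but it is more than a typographical correction, so under Section 15.3.1 it needs ethics committee and regulatory approval. In operation the cost is somewhat more frequent halts and SMC reviews: at the assumed 5%/5% rates, halt probability rises by 0.07 (half of SAEs graded severe) to 0.14 (all graded severe, or counts pooled). Each halt carries the restart submission that Section 4.4.3.2 requires, which could disturb the eight-weekly dosing schedule.
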